6. STUDY PROCEDURES

6.1 Schedule of Evaluations

RCT Assessments

Assessment Name/Domain	Data Source	Baseline	12-wk	36-wk
Socio-demographic Characteristics	Self-Report	x		
Psychiatric and Substance Use Diagnoses	VA EHR -structured data (e.g. clinic codes)	x		
Characteristics of Musculoskeletal Disorders	VA EHR, Service-connection exam	x		
Distance to nearest VA Facility	VA EHR		x	
Brief Pain Inventory	Self-report	x	x	x
Numeric Rating Scale	Self-report	x	x	x
Opioid Medications Dispensed in Morphine Equivalent Daily Dose	VA EHR	x	x	x
Non-opioid Medications Dispensed	VA EHR	x	x	x
Non-pharmacological Pain Management Service Use—VA services	VA EHR -structured data (e.g. clinic codes)	x	x	x
Non-pharmacological Pain Management Service Use---VA and non-VA services	VA EHR with Natural Language Processing	x	x	x
Self-reported VA and non-VA service use	Self-report	x	x	x
ASSIST	Self-report	x	x	x
Prescription Opioid Misuse	Self-report	x	x	x
Nail clippings for drug/etoh use metabolites	Biological	x	x	x
Substance Use Treatment Service Utilization – VA services	VA EHR -workload data and clinic codes	x	x	x
Self-reported VA and non-VA substance use service use	Self-report	x	x	x
PHQ-9 (depression)	Self-report	x	x	x
EQ-5D -5L	Self-report	x	x	x
PEG	Self-report	x	x	x
Motivation for engaging in pain treatment	Self-report	x	x	x

High Impact Pain Questions	Self-report	x		
Audit-C	Self-report	x		
COVID-19 questionnaire	Self-report	x	x	x

UG3 Preparation Assessments and End-of-Study Assessments

Measures Described Earlier in UG3 Stage of RCT preparation	Data Source	UG3 preparation phase	End of Study
Qualitative Interviews of Stakeholders	Self-report	x	x
Post-intervention Interview of SBIRT-PM-treated Veterans	Self-report	x	
Relational Coordination Survey of Key Stakeholders	Self-report	x	x
Treatment Fidelity Measure: Independent Tape Rater Scale	audio recorded SBIRT-PM session ratings		x

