- Alcohol Use Disorders Identification Test (AUDIT-C)¹²⁸. This is an alcohol screen used to identify patients who are hazardous drinkers or have active alcohol use disorders (including alcohol abuse or dependence). It consists of three questions: "how often did you have a drink containing alcohol in the past year?", "how many drinks did you have on a typical day when you were drinking in the past year", and "how often did you have six or more drinks on one occasion in the past year". It is scored on a scale of 0 (no use) through 12. In men, a score of 4 or more is considered positive and in women, a score of 3 or more is considered positive.

Other Measures:

- Patient Health Questionnaire (PHQ-9). The PHQ-9 is a well validated screening measure for depression¹²⁹ and will be used to identify probable depression as a covariate in analyses. It will also identify suicidal ideation, which if severe, will trigger the need for further assessment (detailed in Human Subjects).
- EQ-5D-5L. The EQ-5D-5L is a standardized measure of health status designed to provide a single index value of health for clinical and economic appraisals. It consists of five questions in the domains of mobility, self-care, usual activities, pain/discomfort, and anxiety/depression. ¹³⁰
- Motivation for engaging in pain treatment^{131,132}. Motivation for Change Scale to include 3 items (analogue scale coded from 1 to 100) tapping patient likelihood to engage in pain services, recognition of pain treatments as important, and pain treatment motivation.
- COVID-19 questionnaire. These questions will assess participant infection status, adherence to COVID-19 safety regulations, and the effect that COVID-19 regulations have had on Veterans' social determinants of health, access to pain treatment, and access to substance use treatment.

Qualitative Measures Collected in UG3 Phase and then again at the end of the UH3 Phase:

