7. SAFETY ASSESSMENTS

The risk to Veterans who participate in this study is minimal. Nevertheless, research staff will be trained in the detection and investigation of adverse events during the conduct of study assessments or other interactions with participants.

Expected adverse experiences include:

- Counseling session or study procedures upsets participant
Criteria for management: Careful training of study staff and SBIRT-PM counselors will precede study initiation. If a participant complains about study procedures or counseling sessions, the complaint will be logged and will be brought to the attention of the mPIs. Depending on the nature of the complaint, mPIs will decide whether the complaint requires follow-up directly with the participant.
- Suicidal ideation detected by the PHQ-9 or by counseling
Criteria for management: item 9 in the PHQ-9 identifies potential suicidal ideation (the questions asks about “thoughts of being better off dead or of hurting yourself in some way”). It is collected at baseline and at 12- and 36-week follow-ups. Any positive response (response other than “none at all”) to this question will be further evaluated, as well as other expressions of suicidality to the research assistant or SBIRT-PM clinician. Positive responses will be evaluated by one of the mPIs, Site-PIs, or covering providers. The response to clinical emergencies will be delineated in the Service Use Agreements between the hub site and spoke for provision of SBIRT-PM. If the research team decides that the information must be reported, the person who spoke to the Veteran (clinician or research assistant) will contact the Site-PI from the relevant medical center, and if he or she is not available, the clinician designated by the spoke site for handling mental health crises at the sites. All VISN1 medical centers have emergency room facilities and a suicide prevention coordination team. If the participant’s situation precludes management by spoke personnel (e.g. the Veteran is not accessible to VA staff or the site PI), the Research Assistant will immediately consult with one of the mPIs about ways to handle the situation, including calling for a police safety check on the Veteran.

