7.1 Specification of Safety Parameters

NA.

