9.5.2 Secondary Outcomes

Secondary outcomes related to pain include non-pharmacological pain management service utilization, pain interference with life activities (BPI), overall pain (PEG), and overall health. The non-pharmacological pain management service utilization will be

summed across 13 possible modalities (injection; physical therapy; chiropractic care; acupuncture; TENS; Spinal cord stimulator; cognitive behavioral therapy; mindfulness/acceptance and community therapy; treatment involving teaching about coping with pain; yoga, Tai chi or Reiki; massage treatment; other treatment not already mentioned) as well as examined by individual modalities where sufficient sample size is present.

Secondary outcomes related to substance use will include severity measures for individual substances generated by the ASSIST, as well as toxicology results for individual substances.

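### PHQ-9 item 9 measures suicidal ideation, a named expected harm, in both arms at all three visits, but the plan specifies no by-arm safety comparison of it

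*Combined protocol and SAP*

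**What the plan says.** **The harm and its measure.** Section 7 gives a list of expected adverse experiences with two entries: "Counseling session or study procedures upsets participant" and "Suicidal ideation detected by the PHQ-9 or by counseling". Of PHQ-9 item 9 it says: "It is collected at baseline and at 12- and 36-week follow-ups". The schedule in Section 6.1 agrees and makes no distinction by arm. Under Section 6.2.3 the assessors are blind to assignment, and under Section 6.2.5 participants are followed whether or not they took up counseling.

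**Planned use.** Section 6.2.2 gives the PHQ-9 one analytic role, that it "will be used to identify probable depression as a covariate in analyses", and one clinical role: "It will also identify suicidal ideation, which if severe, will trigger the need for further assessment". Section 9.6 repeats the covariate role by listing depression among the key covariates, without saying which visit's value is meant.

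**Safety and outcome sections.** Under the heading "Specification of Safety Parameters" (Section 7.1) the only entry is NA. Section 7.2 covers recording events and asking about them, not analysing them. In Section 9.5.2, "Secondary outcomes related to pain include non-pharmacological pain management service utilization, pain interference with life activities (BPI), overall pain (PEG), and overall health". The substance-related secondary outcomes do not include depression or ideation either, and neither do the primary outcomes or the comparisons in Section 9.6.

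**The concern.** The plan names a harm, measures it the same way in both arms with a baseline value, and then specifies no comparison. Whatever the trial says about ideation would come from adverse event reports. That route is weaker for two reasons.

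- Section 7.3 excludes exacerbation of symptoms from adverse events and does not list ideation among the anticipated ones. New or worse ideation may therefore never be logged.
- Section 7 allows detection through counseling, which exists only in the SBIRT-PM arm. Event counts could make the intervention look worse than it is, for reasons of detection alone.

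Section 8 also gives adverse effects associated with the intervention as a ground for stopping the study. An association is hard to judge without a view by arm. At stake is the safety statement in the trial report, not the co-primary results.

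**Working it through.** **1. Following item 9 through the plan**

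| Place | What it provides | By-arm result for item 9 or PHQ-9 total? |
|---|---|---|
| 6.1, Section 7 | Collected at baseline, week 12, week 36 | Data only |
| 6.2.2 | Depression covariate; clinical trigger | No |
| 7.1 | NA | No |
| 7.2 | Events recorded and asked about | No |
| 7.3 | Symptom exacerbation not an adverse event | No |
| 7.6 | Annual list and summary of adverse events | None described |
| 9.5.1, 9.5.2 | Primary and secondary outcomes | No |
| 9.6 | Depression as covariate | No |

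**2. The number available**

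The per-arm number comes from Section 9.2: d = 0.25, alpha = .025 (taken as two-sided), power .90. Reproducing it:

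n = 2 × (2.241 + 1.282)² / 0.25² = 2 × 12.41 / 0.0625 ≈ 398 per group, against 400 stated.

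400 / 0.73 = 548 per group, and 548 × 2 = 1096. The plan's figure reproduces and is not in dispute. It supplies about 400 evaluable per arm.

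**3. Precision of a by-arm comparison**

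The documents give no rate of positive item 9 responses, so 5% to 20% is assumed, equal in both arms. Half-width of the 95% confidence interval for the risk difference = 1.96 × √(2p(1−p)/400).

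| Assumed p | Calculation | Half-width (points) | Increase detectable with 80% power, two-sided .05 (points) |
|---|---|---|---|
| 5% | 1.96 × √(0.095/400) | 3.0 | 5.3 |
| 10% | 1.96 × √(0.18/400) | 4.2 | 6.8 |
| 15% | 1.96 × √(0.255/400) | 4.9 | 7.8 |
| 20% | 1.96 × √(0.32/400) | 5.5 | 8.5 |

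This would bound a large shift but not exclude a modest one. By the normal approximation, power for 10% against 15% is about 57%, and for 10% against 13% about 26%. The results should therefore be read as estimates with intervals. These figures are for any positive response; no precision is derived for a newly positive or worse response, because that rate is also unknown.

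**4. Two triggers**

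Section 6.2.2 ties further assessment to severe ideation ("It will also identify suicidal ideation, which if severe, will trigger the need for further assessment"). Section 7 calls for further evaluation after any answer to item 9 other than the one denying such thoughts. The two passages differ and must be reconciled.

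**The case against.** The strongest reply is that the plan treats ideation as something to detect and respond to, not as a hypothesised effect. Section 7 calls the risk minimal, and Sections 7.2 and 9.4 cite an earlier in-person version with no study-related adverse events. Adverse events are asked about at every visit and reviewed monthly and annually. Section 9.6 says all variables, covariates included, will be described. Overall health is a secondary outcome, and the EQ-5D-5L has an anxiety/depression item. This stands as partial cover. None of it is a by-arm comparison of ideation, and the EQ-5D-5L does not ask about suicidality.

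Several limits also stand.

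- The data will not be complete. Section 9.2 allows 27% attrition, and Section 9.6 expects more dropout in usual care and some reluctance to tell an interviewer sensitive things.
- Participants know their arm, although assessors do not.
- Item 9 is a screening response that points to possible ideation. It does not establish it.

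A reader might infer that the trial will not report ideation at all. The documents do not support that. Some cases may enter adverse event summaries, Section 7.6 leaves the format of monitoring reports to a charter not included here, and Section 6.2.2 refers to a Human Subjects text not included here. A reader might also infer that ideation is the main safety question, or one of only two harms recognised. The Section 7 list is not worded as exhaustive, Section 7.3 adds any harm that participants attribute to study procedures, and the plan does not rank the harms.

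**Conclusion.** The point holds as a cheap improvement. A named expected harm is measured in both arms, with a baseline value and blinded assessors, and this document specifies no by-arm comparison of it. The adverse event route is a poorer basis for a safety statement, because of its definition and because detection differs by arm. A comparison would give a 95% interval of about ±3.0 to ±5.5 points, resting on 400 evaluable per arm and an assumed 5% to 20% positive. Nothing here affects the co-primary analyses.

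The depression covariate is a related ambiguity. The plan does not say that a follow-up PHQ-9 value would be used, but it does not rule it out, and such a value could itself be affected by the intervention.

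**What to change.** 1. In Sections 7.1 and 7.2, name PHQ-9 item 9 and PHQ-9 total as safety measures.
2. In Section 9.6, add for weeks 12 and 36, by randomised arm: the proportion with a positive item 9; the proportion newly positive or worse than at baseline; the risk difference with 95% confidence interval for each; and PHQ-9 total adjusted for its baseline value.
3. Show denominators by arm and visit. Apply the plan's multiple imputation as a sensitivity analysis, because more dropout is expected in usual care.
4. Describe item 9 as a screening response, and label these results as safety estimates outside the .025 co-primary tests, shown beside the adverse event listing.
5. State that the depression covariate is the baseline PHQ-9 value.
6. Separately, reconcile the triggers for further evaluation in Sections 6.2.2 and 7. Which one applies is for the investigators to settle.

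The cost is some SAP wording and one extra table from data already scheduled for collection. The downside is a few more estimates that must be kept apart from the efficacy results.

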6.2.3 Blinding

Research assistants who collect study data will be blind to participants' treatment assignment. Veterans will be instructed during the assessments not to tell the research assistant if they are receiving study counseling. To determine if the blind was maintained, the research assistant will be asked to what condition each Veteran was assigned. The PIs and Project Director will not be blind to randomization, as they will be assigning study therapists to participants randomized to the treatment condition, reviewing counseling sessions for quality/fidelity, and conducting monthly supervision with study counselors. The statistician has no contact with the study veterans; she will not be blinded.

6.2.4 Follow-up Visits

Research assistants will schedule telephone follow-up interviews approximately 12 weeks (+ 4 weeks) and 36 weeks (+ 4 weeks) after baseline visits. A 4-week window for follow-up appointments allows for flexibility in scheduling and provides sufficient time to complete assessments if an appointment is missed.

Week 12 Follow-up

See schedule of evaluations table and descriptions above.

- Distance to nearest VA Facility. We will calculate the driving distance from the Veterans' address to the nearest VA medical facility providing integrated pain services care services. Calculations will be done using google maps.

Week 36 Follow-up

See schedule of evaluations table and descriptions above.

End-of-Study

- Qualitative interview of stakeholders
- Relational Coordinator survey of key stakeholders
- Treatment fidelity: Independent Tape Rater Scale

6.2.5 Completion/Final Evaluation

Participants' final visit is the Week 36 follow-up. Participants will be contacted for week 12 and 36 follow-up visits regardless of whether they engaged in study counseling. If the 12-week follow-up visit is missed and not completed within 4 weeks of the appointment date, that follow-up will be missed and participant will be contacted for final week 36 follow-up visit.

Participation in study assessments and study counseling is voluntary.

Participants can participate in study assessments and choose not to engage in counseling. Reasons for terminating a participant prior to week 36 are:

- Participant is found to not be eligible for the study after enrollment
- Participant withdraws consent for further contact

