Staff obtaining verbal consent will have completed a web-based course with post-test on Human Research Protections, and all will have had specific training by the mPIs in obtaining informed consent for this project. All staff obtaining consent will be authorized to do so by the VA Central IRB.

Justification for obtaining a waiver of documentation of informed consent and waiver of HIPAA Authorization: These waivers are necessary to conduct the study. The purpose of this study is to test the usefulness of remotely delivered counseling. All counseling sessions and research assessments are conducted remotely. There is no face-to-face contact with participants and the study is considered minimal risk. It would be burdensome and impractical to have potential participants come in to the VA just to sign a study Consent Form and HIPAA authorization. This study could not practically be conducted without the waivers due to the timing of study procedures. Baseline assessments and study counseling should occur before or within six weeks after the recruitment letter is mailed. Waiting for the Veteran to find time to come to the VA to sign a Consent Form and HIPAA Authorization or waiting for the Veteran to return a signed copy of the Consent Form and HIPAA Authorization by mail will likely push the timing of study assessments outside of this window, making a large proportion of eligible Veterans ineligible.

Randomization: The unit of randomization is participant. Participants will be randomized to SBIRT or Usual Care using a computerized urn randomization program⁹⁰ within each site to increase the likelihood of balanced allocation of participants to the two interventions on sex, race (Caucasian, African American), ethnicity (Hispanic no/yes) and self-reported illicit drug use within 90 days. The research assistant will be blind to the assigned condition. For each participant, Research Assistants will communicate data needed for the urn to the Project Director, who will randomize the participant and assign a study therapist based on location, availability and work flow.

Enrollment: Participants are considered enrolled after they complete the informed consent process and agree to study procedures.

Informed Consent and Enrollment for VA Staff:

A waiver of documentation of Informed Consent for VA Staff participants has been obtained for staff participants.

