- Relational Coordination Survey. This survey, will be administered post-trial to "hub" SBIRT-PM clinicians and "spoke" clinical and administrative staff in Compensation and Pension and Primary Care to examine how pain care was coordinated to meet the treatment needs of compensation-seeking Veterans. It includes seven dimensions: frequency of communication, timeliness of communication, accuracy of communication, problem-solving, shared goals, shared knowledge, mutual respect). Respondents indicate the frequency in which each dimension exists in their setting on a 5-point scale. The mean of the individual scores serves as the overall RC score for each dimension within each spoke site.
- Post-Trial Semi-Structured Qualitative Interview. At the end of the trial, we will conduct in-depth interviews with "hub" SBIRT clinicians and "spoke" clinical and administrative staff in Compensation and Pension and Primary Care to assess the organization and coordination of pain management services, given their experiences with SBIRT-PM implementation.

Randomization

The urn randomization covariates are: site (8 sites of VISN1), sex (M/F), race (White, Black, Other), ethnicity (Hispanic/Non-Hispanic), and self-reported illicit drug use (Yes/No). Following enrollment and Baseline assessments, the Project Director will enter covariates into urn randomization program to determine intervention condition assignment. Randomization will occur within two weeks of the enrollment date.

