7.6 Safety Monitoring

A Data and Safety Monitoring Committee (DSMC) will be appointed by NCCIH to review study progress, assess the adequacy of ongoing enrollment & site performance, ensure adequacy of data acquisition & protocol adherence and evaluate overall safety throughout trial implementation. The DSMC will meet at least annually after trial initiation. A DSMC Charter Document outlining the operating guidelines for the committee, the frequency of planned meetings and the specific data presentation format will be agreed upon during the initial meeting of the DSMC. Study reports will be created by the study data center, following a standardized format, as directed by the DSMC. The DSMC will report directly to NCCIH.

Study progress and safety will be reviewed annually during the RCT. Progress reports, including patient recruitment, retention/attrition, and AEs will be provided to the DSMB annually. This Annual Report will include a list and summary of AEs. In addition, the Annual Report will address (1) whether AE rates are consistent with pre-study assumptions; (2) reason for dropouts from the study; (3) whether all participants met entry criteria; (4) whether continuation of the study is justified on the basis that additional data are needed to accomplish the stated objectives of the study; and (5) conditions whereby the study might be terminated prematurely. The Annual Report will be sent to the Independent Monitor(s) and will be forwarded to the VA Central IRB and the NCCIH Program Officer within 1 month of each monitoring review.

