9.3 Definition of Populations

The study will occur within the eight VISN-1 VA medical centers (VAMC) located across six New England States. The medical centers are: Bedford VAMC; Boston Healthcare System; Central Western Massachusetts; Connecticut Healthcare System; Maine Healthcare System, Manchester VAMC, Providence VAMC, and White River Junction.

Inclusion and exclusion criteria:

Inclusion criteria: 1) post-9/11 Veteran applying for MSD-related compensation (specified as back, neck, shoulder, or knee pain), as ascertained from filed claim, 2) reports a score of ≥ 4 (threshold for moderately severe pain) on the BPI's Pain Severity subscale (average of four pain intensity items); 3) availability of a landline or cellular telephone for SBIRT-PM.

Exclusion criteria: 1) reports inability to participate during the study enrollment call; 2) received three or more non-pharmacological pain treatment modalities within the last 12 weeks from VA, and 3) participation in another PMC3 study as evidenced by a research protocol alert for that study at the time the study invitation letter is mailed.

Participants who complete the baseline assessment and are randomized to their treatment assignment will be the Intent to treat (ITT) population for analysis. The per-protocol analyses will specify patients who participated the treatment and be conducted by including a variable indicating participation (Yes/No) in the ITT analyses. We will give precedence to the results of the ITT analysis over the PP analysis.

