10.3.3 Metrics

Study progress and safety will be reviewed monthly by the mPIs and Project Director. An Annual Report will be sent to the Independent Monitor(s) and will be forwarded to the VA Central IRB and the NCCIH Program Officer within 1 month of each monitoring review.

Data type	Frequency of review	Reviewer
Subject accrual (including compliance with protocol enrollment criteria)	Monthly	PI, Project Director
	Annually	DSMB
Status of all enrolled subjects, as of date of reporting	Monthly	PI, Project Director
	Annually	DSMB
Data entry quality control checks on 10% of charts These checks will consist of verifying that there is no missing data (except for patient refusals for specific items) and all assessments are completed. In REDCap, if a question is not answered, a box will pop up highlighting the unanswered questions before it allows the RA to "complete" the form. This will allow veterans to answer any missing items	Monthly	Project Director

during the same telephone call. If a question is refused by the veteran it will be left blank and the RA will put a note in saying it was refused.		
Adherence data regarding study visits and intervention	Monthly	PI, Project Director
	Annually	DSMB
AEs and rates	Monthly	PI, Project Director
	Annually	DSMB
	Annually	NCCIH, VA Central IRB
SAEs (unexpected and related)	Per occurrence	PI, DSMB, NIH/NCCIH
SAEs (expected or unrelated)	Per Occurrence	PI, Project Director
	Annually	DSMB, NIH/NCCIH
Unanticipated Problems	Per Occurrence	PI, Project Director
	Per Policy	VA Central IRB

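### The rule that ends participation for ineligibility found after enrollment is not limited to the period before randomization, so it can create avoidable missing outcomes in the ITT population

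*Combined protocol and SAP*

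**What the plan says.** Section 6.2.5 introduces a short list with "Reasons for terminating a participant prior to week 36 are" and gives two entries: withdrawal of consent for further contact, and "Participant is found to not be eligible for the study after enrollment". The same section promises that "Participants will be contacted for week 12 and 36 follow-up visits regardless of whether they engaged in study counseling".

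The timing comes from two other places. Section 4.3 states that "Participants are considered enrolled after they complete the informed consent process and agree to study procedures", so enrollment means consent. Section 6.2.2 puts allocation after enrollment and the baseline assessments and adds that "Randomization will occur within two weeks of the enrollment date".

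Section 9.3 defines the analysis set: "Participants who complete the baseline assessment and are randomized to their treatment assignment will be the Intent to treat (ITT) population for analysis". It makes no exception for ineligibility found later.

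Eligibility is checked throughout the trial. The table in Section 10.3.3 has the PI and Project Director review accrual monthly, including compliance with the enrollment criteria. The Annual Report in Section 7.6 covers "whether all participants met entry criteria". Section 6.2.3 says that the PIs and Project Director are not blind to allocation.

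**The concern.** The termination rule and the ITT definition do not fit together once a participant has been randomized. Section 9.3 counts that person in the analysis, but Section 6.2.5 lets the study stop collecting the outcomes that the analysis needs. Nothing in the documents says that a randomized participant found ineligible is still assessed, that the eligibility decision may use only information from before randomization, or that it is made blind to arm.

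This differs from ordinary dropout. The Veteran has consented and may still be reachable by telephone; the loss comes from a study decision. Two features could make discovery differ by arm. The staff who review eligibility compliance know the allocation. And only SBIRT-PM Veterans have counselors who discuss pain care with them and who, under Section 5.1, may draw on primary care team contacts and the health record. At stake is the completeness of the ITT comparison on both primary outcomes.

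**Working it through.** **1. When the clause can act.** Consent is enrollment; baseline follows; randomization comes within two weeks of enrollment; follow-up then runs to about week 36. Most of the period that the clause covers therefore lies after randomization.

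| Ineligibility found | In ITT (Section 9.3)? | Outcomes lost |
|---|---|---|
| After consent, before randomization | No | None that matter |
| After randomization, before the week-12 assessment | Yes | Week 12 and week 36 |
| After the week-12 assessment, before week 36 | Yes | Week 36 only |

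Only the last two rows are a problem. In the third row the week-12 BPI value, which Section 9.6 expects to model, is kept. The documents do not say whether outcomes taken from records also stop at termination.

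**2. The plan's sample size (Section 9.2), reproduced.** Inputs: d = 0.25, alpha = 0.025 per primary outcome (two-sided, which is the reading that reproduces the figure), power 0.90, attrition 27%.

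- n per group = 2(z₀.₉₈₇₅ + z₀.₉₀)² / d² = 2(2.241 + 1.282)² / 0.0625, giving 398 against the stated 400.
- 400 / 0.73 = 548 per group; 548 × 2 = 1096, planned as 1100.

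The sample size is not in dispute.

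**3. Effect on power.** With 1100 randomized and 27% lost, 1100 × 0.73 / 2 = 401.5 per arm remain, and power for pain severity is 90.3%. The documents give no rate of late ineligibility, so the extra losses below are assumptions.

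| Extra loss | Power |
|---|---|
| 1% of both arms | 90.0% |
| 2% of both arms | 89.7% |
| 5% of both arms | 88.7% |
| 5% of SBIRT-PM only | 89.5% |

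Power hardly moves.

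**4. Effect on the estimate.** Suppose a share x of one arm is removed and the mean of those removed differs by g SD from the mean of the whole arm. The mean of those who remain, and so the complete-case contrast, shifts by x·g / (1 − x). With g = 0.5 SD (assumed) and 550 randomized per arm:

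| x | Participants (550·x) | Shift (SD) | Share of d = 0.25 |
|---|---|---|---|
| 1% | 5.5 | 0.01 × 0.5 / 0.99 = 0.005 | 2% |
| 2% | 11 | 0.02 × 0.5 / 0.98 = 0.010 | 4% |
| 3% | 16.5 | 0.03 × 0.5 / 0.97 = 0.015 | 6% |
| 5% | 27.5 | 0.05 × 0.5 / 0.95 = 0.026 | 11% |

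A harsher case, x = 5% with g = 1.0 SD, gives 0.05 × 1.0 / 0.95 = 0.053 SD, or 21% of d.

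**5. What imputation can do.** Section 9.6 plans multiple imputation under MCAR or MAR with auxiliary variables. Arm is always observed. If discovery depends on arm and on other observed variables, such as the number of modalities used at baseline, the missingness is MAR, and an imputation model containing those variables handles it. Bias remains only where discovery is also related to unobserved outcomes. The shifts in step 4 are for a complete-case contrast.

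**The case against.** The strongest defence is that the clause has a natural and harmless use. Screening is brief (Section 6.2.1). The baseline battery then repeats the BPI and adds a detailed service-use questionnaire covering the past 3 months, and allocation comes afterwards. Ineligibility found after enrollment would most naturally surface there, before randomization, and those people never enter the ITT set. The other criteria (a filed claim, a telephone, ability to participate, a research alert at mailing) leave little to discover later. That reading is reasonable, but the text does not confine the clause to it, and the list governs termination at any time up to week 36.

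Some monitoring also exists already: Section 7.6 reports reasons for dropout and whether entry criteria were met, and Sections 10.2 and 10.3.5 check attrition by treatment monthly. This helps to detect the loss but does not recover the missing outcomes.

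A reader might infer three stronger things that the documents do not support.

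- *Late discovery is likelier in the SBIRT-PM arm.* This is possible but not shown. Counselors have no stated role in checking eligibility; Section 5.1 describes their record review as a support for follow-up calls. Use of three or more VA modalities would tend to appear at baseline in both arms, before any allocation exists.
- *Imputation cannot repair the loss because discovery depends on arm.* Dependence on arm alone is MAR, as step 5 of the working shows.
- *The ITT analysis is broken, or the outcomes are never collected.* Section 9.3 removes nobody, and week-12 data survive a later termination. The defect is avoidable missing data within an intact ITT set.

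**Conclusion.** The point holds as an inconsistency between a stated rule and the stated analysis population. As written, Section 6.2.5 allows the study to end follow-up of randomized participants whom Section 9.3 retains, and no other text prevents it.

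The likely size is small. On assumed removal of 1% to 5% of one arm with a 0.5 SD difference, the complete-case shift is about 0.005 to 0.026 SD, and imputation that includes arm and baseline predictors should reduce any part explained by observed variables. The frequency, direction and arm balance of such terminations are all unknown from the documents. It is a cheap improvement: worth making because the loss is self-imposed and the change costs almost nothing.

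**What to change.** 1. In Section 6.2.5, limit the ineligibility reason to participants who have not yet been randomized.
2. State there and in Section 9.3 that a randomized participant later found ineligible stays in follow-up at weeks 12 and 36, and in the ITT analysis, unless consent is withdrawn.
3. Report late-ineligibility counts, timing and reasons by arm.
4. Section 9.5.1 already gives week-36 nail-return figures, so follow-up is over for some participants. Where that is so, keep anyone terminated under this clause in ITT with all data collected, and include arm and the baseline modality count in the imputation model.

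Cost: one or two protocol sentences, one reporting table, and possibly a few extra telephone interviews.
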